6.5 Prior and concomitant therapy

All medication that is considered necessary for the subject's welfare, and which is not expected to interfere with the evaluation of the study treatment, may be given at the discretion of the investigator. All medications (including contrast media) taken within 2 weeks prior to the start of the study and during the study must be recorded in the subject's source documentation and in the CRF (including start/stop dates, dose frequency, route of administration, and indication). Specific caution should be taken when considering or administering a concomitant medication that is metabolized by the cytochrome enzymes CYP2C8, CYP2B6 and CYP2C9. Such concomitant medication should be avoided, if possible.

Co-administration of a strong CYP3A4 inducer (rifampin) with a single 160 mg dose of Stivarga decreased the mean exposure of regorafenib, increased the mean exposure of the active metabolite M-5, and resulted in no change in the mean exposure of the active metabolite M-2. Avoid concomitant use of Stivarga with strong CYP3A4 inducers (e.g. rifampin, phenytoin, carbamazepine, phenobarbital, and St. John's Wort)

Co administration of a strong CYP3A4 inhibitor (ketoconazole) with a single 160 mg dose of Stivarga increased the mean exposure of regorafenib and decreased the mean exposure of the active metabolites M-2 and M-5. Avoid concomitant use of Stivarga with strong inhibitors of CYP3A4 activity (e.g., clarithromycin, grapefruit juice, itraconazole, ketoconazole, nefazadone, posaconazole, telithromycin, and voriconazole).

Permitted concomitant therapy includes:

- Standard therapies for concurrent medical conditions.
- Supportive care for any underlying illness.
- Palliative radiation therapy is allowed if the target lesion(s) are not included within the radiation field and no more than 10% of the bone marrow is irradiated.
- Granulocyte colony-stimulating factor (G-CSF) and other hematopoietic growth factors may be used in the management of acute toxicity, such as febrile neutropenia, when clinically indicated or at the investigator's discretion. However, they may not be substituted for a required dose reduction. Subjects are permitted to take chronic erythropoietin.
- Treatment with nonconventional therapies (such as acupuncture), and vitamin/mineral supplements are permitted provided that they do not interfere with the study endpoints, in the opinion of the investigator.
- Bisphosphonates

- As the study requires tissue biopsies, subjects that are therapeutically treated with an agent such as warfarin or heparin will not be allowed to participate in the trial. However, patients that require anticoagulation after the biopsies are obtained can continue on the study. The following are not permitted:
- Other investigational treatment during or within 30 days before starting study treatment
- Systemic antitumor therapy, including cytotoxic therapy, signal transduction inhibitors, immunotherapy, and hormonal therapy
- Bone marrow transplant or stem cell rescue
- Subjects taking narrow therapeutic index medications should be monitored proactively (e.g. warfarin, phenytoin, quinidine, carbamazepine, Phenobarbital, cyclosporin, and digoxin). Warfarin is metabolized by the cytochrome enzyme CYP2C9 and its levels may be especially affected by regorafenib
- Use of any herbal remedy (e.g. St. John's wort [*Hypericum perforatum*])
- Please note: Patients should be seen frequently / early during treatment as per Prescribing Information
- Liver function tests should be obtained before initiation of regorafenib and monitored at least every 2 weeks during first 2 months of treatment. Thereafter liver function should be monitored monthly or more frequently as clinically indicated
- Monitor blood pressure weekly for the first 6 weeks of treatment and every cycle or more frequently as clinically indicated.

7. Detailed Study Plan

7.1 Screening

Screening will occur within 28 days prior to administration of the first dose of chemotherapy on Day 1. Signed informed consent will be obtained from the subject or the subject's legally acceptable representative before any study-specific procedures are undertaken. For procedures performed at screening and repeated, the later procedure performed prior to dosing will serve as a baseline for clinical assessment. A complete history and physical will be obtained at the screening visit. Additionally, labs will be reviewed/ordered during the screening visit, prior to the initiation of therapy.

7.2 Study Procedures (details are provided in the events table (Page 42))

7.2.1 Subject assessments

Physical examinations (including neurological assessment), vital signs (vital sign determinations include heart rate, blood pressure and body temperature - *Vital signs should be taken after a 5-minute resting period. Labs will then be drawn once the vital signs are recorded*), performance status, chemistry, hematology, medication review, and adverse event evaluations will be conducted at screening, on C1D1, C1D14, C2D1, C2D14, D1 of every cycle starting C3, and at the off study visit. Study procedures may be performed 2 days before the scheduled visit date, due to unforeseen or unavoidable circumstances.

Body weight will be recorded during every physical exam. The subject will wear lightweight clothing and no shoes during weighing. Height will be measured at the Screening Visit only; the subject will not wear shoes.

30 days after the patient's "end of treatment" visit; a 30-day follow-up patient survival assessment will be made by [contact] Tumor Imaging and Response Evaluation

Baseline imaging (CT scan) will be carried out for all cohorts within 28 days prior to regorafenib therapy—and then must be performed every 8 weeks (as near to Day 1 as possible; every 2 cycles) following initiation of regorafenib treatment.

7.2.1.2 Medical History

The following information will be collected during the Screening Visit:

- 1) Complete medical history, including documentation of any clinically significant medical conditions
- 2) History of tobacco and alcohol use
- 3) Presence and severity of any symptoms/conditions associated with metastatic colorectal cancer
- 4) Detailed oncology history, including:
 - a. Date of primary cancer diagnosis
 - b. Pathology (histology or cytology) of primary tumor
 - c. Metastasis information (including the location)
 - d. Surgical history
 - e. Anti-cancer and radiation treatments administered (including dates and type of modality)

7.2.1.3 Research Samples

Tumor biopsies will be obtained at baseline—prior to treatment initiation—and on day 14-21 of therapy (cycle 1). Peripheral blood collection for research purposes will occur at baseline, on day 14-21 of therapy (on day of tumor biopsy; cycle 1) and then on D1 of each cycle starting C3 (i.e., every 4 weeks starting cycle 3) up to 8 blood draws while taking regorafenib on study.

7.2.1.4 Pregnancy Test

For female subjects of childbearing potential, a serum pregnancy test will be performed at the Screening Visit within 28 days of C1D1. Subjects considered not of childbearing potential must be documented as being surgically sterile or post-menopausal (for at least 1 year). The test results must be reviewed and determined to be negative prior to dosing. The test may be repeated at the discretion of the investigator at any time during the study. Should a female study subject become pregnant or suspect she is pregnant while participating in this study, she should inform the treating Investigator immediately.

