- Women of childbearing potential must have a negative serum pregnancy test performed within 7 days prior to the start of study drug. Post-menopausal women (defined as no menses for at least 1 year) and surgically sterilized women are not required to undergo a pregnancy test. Subjects (men and women) of childbearing potential must agree to use adequate contraception beginning at the signing of the ICF until at least 3 months after the last dose of study drug. The definition of adequate contraception will be based on the judgment of the principal investigator or a designated associate but is generally defined as a hormonal or barrier method of birth control, or abstinence.
- Subject must be able to swallow and retain oral medication.

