5.3.2 Patient Enrollment

Enrollment at the sites will be competitive. If a patient is being screened for enrollment, the local research coordinator must send an email within 24 - 48 hours containing the subject number, to the PI, and to the multi-institutional coordinator. If a patient is successfully screened, the local research coordinator must send all supporting documentation to the multi-institutional research coordinator (by email [[contact]]). Patients should not start therapy until both PI and the multi-institutional coordinator have reviewed the patient’s records and confirmed that the patient is indeed eligible for enrollment.

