7.2.1.10 Tumor Biopsies

The second tumor biopsy (at 2-3 weeks) can be waived in case of patient refusal, complications after the first biopsy or if the investigator deems the biopsy unsafe.

Tumor samples obtained at Georgetown Hospital and other sites will be collected by the staff of the biospecimen bank. Two specimens will be placed in biopsy cassettes embedded in optimal cutting temperature compound (OCT) and snap frozen within 15 min in dry ice or liquid nitrogen and subsequently stored at -80 until further use. The OCT embedded frozen core needle biopsy samples will be stored in the Georgetown University laboratory then shipped to the laboratory of [name] (George Mason University, [name]; Email: [contact]; [contact]) via FedEx medical shipment service after the last sample has been obtained or two years after the first sample has been obtained whichever occurs first. Once at George Mason University tissue-based laser capture microdissection and protein pathway activation mapping via reverse phase protein array analysis will take place. The rest of the samples will be placed in formalin and then paraffin blocks will be formed to be sent to Caris for CMI testing. Only the baseline tumor samples should be sent to Caris. Please see Appendix 14.1 for specimen requirements.

EVENTS TABLE and STUDY CALENDAR

Baseline evaluations are to be conducted within 28 days prior to start of protocol therapy. Scans and x-rays must be done ≤ 4 weeks prior to the start of therapy. Unless otherwise noted, a standard window of -1 day to + 2 days will be considered acceptable for all testing and evaluations (will not be considered study deviation). In the event that the patient's condition is deteriorating, laboratory evaluations should be repeated within 48 hours prior to initiation of the next dose of therapy.

	Screening Day -28 to -1	C1D1 & C2D1	Day 1 - 21 of every Cycle; starting C1	C1 D 14- 21	C1D14 & C2D14	Day 1 of each cycle starting cycle 2	Every 8 weeks	Disease progression or end of treatment ⁸
Informed consent	X							
Demographics	X							
Medical history	X							
Concurrent meds	X	X			X	X		X
β -HCG ¹	X							
Physical Exam	X	X			X	X		X
Vital signs	X	X			X	X		X
Height	X							
Weight	X	X			X	X		X
Performance status	X	X			X	X		X
Oral Regorafenib		X	X		X	X		
CBC with diff	X	X			X	X		X
Serum chemistries ²	X	X			X	X		X
PT/INR/PTT ⁷	X							
CEA ³	X	X				X		X

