Adverse event evaluation	X	X			X	X		X
Radiological evaluation and tumor measurement ⁴	X						X	X ⁵
Research Biopsy	X			X				
Research serum samples ⁶	X			X		X		X

¹ A serum pregnancy test (women of child bearing potential) at screening only. However, the test may be repeated at the discretion of the investigator at any time during the study.

² Serum chemistry will include sodium, potassium, chloride, BUN, bicarbonate creatinine, AST, ALT, total bilirubin, direct bilirubin, albumin, total protein and alkaline phosphatase

³ CEA should be taken on D1 monthly

⁴ Tumor measurements will be obtained by CT scan (or MRI at physician discretion) using RECIST criteria. If patient insurance will not cover a CT/MRI scan within 14 days of regorafenib treatment then a scan within 4 weeks of treatment is acceptable.

⁵ Only if not performed within the last 4 weeks

⁶ Patients will undergo peripheral blood collection for research purposes every 4 weeks for up to 8 blood draws (if still actively on study for that long)

⁷ PT/INR/PTT is only performed at screening unless especially required at 4 weeks by the investigator.

⁸ 30 days after the patient's "end of treatment" visit, a 30-day follow-up patient survival assessment will be made by phone.

8. Endpoints

8.1 Primary endpoint:

8.1.1 Level of serum miRNAs at baseline, 4 and 8 weeks of study treatment

8.2 Secondary endpoints:

8.2.1 Eight-week clinical benefit rate (CBR):

Defined as proportion of patients who achieve completed response (CR) any time + partial response (PR) any time + stable disease (SD) at 8-week and will be measured every eight weeks based on the RECIST criteria version 1.1.

8.2.2 Objective response rate (ORR):

Will follow the RECIST criteria version 1.1 and will be defined as partial response (PR) or complete response (CR). Patients who are lost to follow-up without a valid response assessment will be classified as non-responders.

8.2.3 Progression free survival (PFS):

Defined as the number of days from study entry until progression or death; patients who are alive and free from progression on the date of closing follow-up will be censored on that date.

8.2.4 Overall survival (OS):

Defined as the time in days from study entry until death; patients who are alive on the date of closing follow-up will be censored on that date. All events of death will be included.

8.2.5 Safety:

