8.4.6 Pregnancies/Contraception

The effects of regorafenib on the developing human fetus at the recommended therapeutic dose are unknown. Regorafenib was embryo-lethal and teratogenic in rats and rabbits at exposures lower than human exposures at the recommended dose, with increased incidences of cardiovascular, genitourinary, and skeletal malformations. For this reason, women of child-bearing potential and men must agree to use adequate contraception (hormonal or barrier method of birth control; abstinence) prior to study entry and for the duration of study participation.

The investigator must report to Bayer any pregnancy occurring in a study subject, or in his partner, during the subject's participation in this study. The report should be submitted within the same timelines as an SAE, although a pregnancy per se is not considered an SAE.

For a study subject, the outcome of the pregnancy should be followed up carefully, and any abnormal outcome of the mother or the child should be reported.

For the pregnancy of a study subject's partner, all efforts should be made to obtain similar information on course and outcome, subject to the partner's consent.

For all reports, the forms provided are to be used.

9. Statistical methods and determination of sample size

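### Eligibility requires a negative serum pregnancy test within 7 days before study drug, but Section 7.2.1.4 and the study calendar schedule one test up to 28 days before, with no required repeat

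*Combined protocol and SAP*

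**What the plan says.** Three places in the combined protocol and SAP set the timing of the pregnancy test.

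- **Section 5.1.1, Inclusion criteria.** Women of childbearing potential "must have a negative serum pregnancy test performed within 7 days prior to the start of study drug".
- **Section 7.2.1.4, Pregnancy Test.** For the same women, "a serum pregnancy test will be performed at the Screening Visit within 28 days of C1D1". The result must be reviewed and found negative before dosing. A repeat is allowed at the investigator's discretion.
- **Events Table and Study Calendar (after Section 7.2.1.10).** The general rule is: "Baseline evaluations are to be conducted within 28 days prior to start of protocol therapy". The β-HCG row is marked only in the screening column, which runs from day -28 to day -1. Footnote 1 reads: "A serum pregnancy test (women of child bearing potential) at screening only". It continues: "However, the test may be repeated at the discretion of the investigator at any time during the study".

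Two other provisions bear on the risk. Section 5.3.2 states: "Patients should not start therapy until both PI and the multi-institutional coordinator have reviewed" the records and confirmed that the patient is eligible. Section 5.1.1 also says that subjects of childbearing potential "must agree to use adequate contraception beginning at the signing of the ICF".

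**The concern.** The inclusion criterion sets a 7-day limit on the age of the test. The sections that a coordinator works from when booking visits set a 28-day limit, and the calendar footnote points away from a second test. A site that follows Section 7.2.1.4 and the calendar to the letter could give the first dose to a woman whose only negative result is up to four weeks old, and who is therefore ineligible under Section 5.1.1.

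What is at stake is patient safety and protocol compliance. Section 8.4.6 reports: "Regorafenib was embryo-lethal and teratogenic in rats and rabbits at exposures lower than human exposures at the recommended dose". Pregnancy is an exclusion criterion (Section 5.1.2) and a mandatory reason for withdrawal (Section 5.2.1). Section 5.2.3 replaces only patients who withdraw before the first biopsy, and that biopsy precedes treatment. A patient withdrawn for a pregnancy found after dosing would therefore not be replaced in a study of 40.

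**Working it through.** The plan gives no figure to reproduce, so the check compares the permitted test days. C1D1 is the first day of regorafenib.

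**Inputs**

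| Source | Permitted test days | Repeat |
|---|---|---|
| Section 5.1.1 | day -7 to day -1 | implied if the test is older than 7 days |
| Section 7.2.1.4 | up to 28 days before C1D1 | discretionary |
| Calendar screening column and footnote 1 | day -28 to day -1 | discretionary |

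**Counting days**

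1. Days permitted by the calendar: day -28 to day -1 = 28.
2. Days that also satisfy Section 5.1.1: day -7 to day -1 = 7.
3. Days that satisfy the calendar and Section 7.2.1.4 but fail Section 5.1.1: 28 - 7 = 21 (day -28 to day -8).
4. Share of permitted days on which a single test fails eligibility: 21 / 28 = 75%.

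**Sensitivity to the counting rule.** If a pre-dose test on C1D1 itself also counts, there are 29 possible days, 8 of them compliant. The failing days remain 21, and the share is 21 / 29 = 72%. The calendar's general tolerance of -1 to +2 days could move an edge by a day or two, but it cannot close a gap of 21 days.

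**Does any other text close the gap?**

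- Section 7.2.1.4 requires a negative result before dosing, but limits its age only to 28 days.
- Section 7.1 says that when a screening procedure is repeated, the later one serves as baseline. It does not require a repeat.
- Section 7.2.1.5 and the calendar schedule hematology and chemistry again on C1D1. The pregnancy test is not scheduled there.
- Section 5.3.2 requires confirmation of eligibility before therapy, but sets no maximum interval between that confirmation and C1D1. A test that is in date at the review could be out of date at the first dose.

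None of these puts the 7-day limit, or a mandatory repeat, into the procedures or the calendar.

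**The case against.** The strongest reply is that the rules are nested and do not contradict each other. A narrow eligibility limit sits inside a wide screening window, a test in the last week satisfies both, and nothing says that a negative result older than 7 days is enough to dose. Section 12.1 demands strict adherence to everything the protocol specifies, so the 7-day criterion binds whatever the calendar shows.

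There are also several safeguards. The principal investigator and the multi-institutional coordinator confirm eligibility against the inclusion criteria, and that coordinator screens every patient, including remotely for other sites (Section 5.3.1). Screening data are to be entered before therapy starts (Section 5.3.3), so the test date should be visible. Pregnancy is excluded in its own right, and contraception is required from consent. Harm would need an old test, no repeat, a date missed at review, and a pregnancy despite contraception.

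Much of this stands. The texts can be met together, the 7-day rule is in force, and the safeguards lower the risk. The 75% describes the calendar and says nothing about how often a patient would be affected.

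It does not dispose of the point. The protocol states no order of precedence between the criterion and the procedures. Section 7.2.1.4 gives a 28-day window specific to this test, which is more than silence about the 7-day limit. The eligibility review would have to reject a test date that the procedures and the calendar both allow. The demand for strict adherence cuts both ways, because a site that adheres strictly to Section 7.2.1.4 can still breach Section 5.1.1.

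**Conclusion.** The inconsistency is real and lies in current text. A single test on any of 21 of the 28 screening days (75%) satisfies Section 7.2.1.4 and the calendar yet fails the inclusion criterion, and no repeat is required.

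It is minor. It affects only women of childbearing potential among the 40 patients, a number the documents do not give, and the documents do not show how long before C1D1 the test is usually taken. No count of patients at risk can therefore be derived. Endpoints, analysis sets and the sample size are not materially affected. The day count assumes the calendar's screening column of day -28 to day -1.

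The correction is worth considering because the rule protects against fetal exposure to a drug that was teratogenic in animals, and because several sites enroll and need one instruction.

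**What to change.** Keep the 7-day limit of Section 5.1.1 and state it in Section 7.2.1.4 and in calendar footnote 1. Suggested wording: *Serum pregnancy test at screening; if it is more than 7 days old at C1D1, repeat the serum test and confirm a negative result before the first dose.* Delete the restriction to screening only from footnote 1, and keep the discretionary repeat for later in the study.

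Do not resolve the mismatch by widening Section 5.1.1 to 28 days, which would weaken the safety rule.

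The cost is wording in two places and at most one further blood test per woman of childbearing potential. Section 5.1.1 already requires that test when the first is older than 7 days, and Section 7.2.1.4 already permits it.

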7.2.1.5 Clinical Laboratory Tests

All subjects will undergo the laboratory assessments outlined in the events table.

- 1) Hematology and chemistry samples will be collected at the Screening Visit, on C1D1, C1D14, C2D1, C2D14, D1 of every cycle starting C3, and at the off study visit. For Day 1 of each cycle after Cycle 1, hematology and chemistry samples may be collected up to 48 hours prior to the scheduled visit.

- 2) A CEA will be collected on Day 1 of every cycle

Clinical laboratory samples for this study will be assessed using the certified laboratories at Georgetown University and affiliated Medstar Hospitals; OR any CLIA-certified laboratory such as LabCorp or Quest is acceptable. The PI or sub-investigator will review, initial and date all laboratory results. Any laboratory value outside the reference range that is considered clinically significant by the investigator will be followed as appropriate. Clinically significant laboratory values will be recorded as adverse events if they meet the criteria as specified in Section 9.4.

